All of these advances in treatment planning and delivery have allowed the development of stereotactic body radiation therapy (SBRT) as a promising treatment for early stage NSCLC. This treatment method combines the previously mentioned techniques with stereotactic targeting to allow a dramatic reduction in treatment volumes, enabling delivery of hypofractionated, ablative doses of radiation therapy. SBRT can be safely used in patients with co-morbid conditions or poor performance status and can achieve local control rates as high as 95% at 2 years [17]. The technological advances making possible SBRT in early stage NSCLC could be transferred to treatment of locally advanced NSCLC as well, to allow a shorter overall treatment time without increasing toxicity. Notably, the reported dose escalation trials for locally advanced NSCLC utilize 3-D conformal radiation therapy but do not include daily image guidance or methods for compensating for tumor motion with respiration. With these technological advances, it should be possible to further limit dose to normal tissue and thus treat lung tumors to a higher dose in fewer fractions of radiation therapy. This protocol will address the management of stage II-III NSCLC who are not candidates for surgical resection or stereotactic body radiation therapy as definitive treatment.

The study is designed to determine whether an accelerated course of hypofractionated radiation therapy with daily image guidance and motion assessment/control will allow more effective treatment of poor performance status patients with stage II-III NSCLC, who would benefit from local therapy compared to standard radiation therapy (60 Gy in 2 Gy per fraction). Poor performance status patients can be a heterogeneous group, with tumor-related factors, other co-morbidities, or advanced age placing patients in the category. These patients have traditionally been underrepresented in clinical trials, and thus no prospective study has evaluated the efficacy of other radiotherapy dose fractionations in these patients. One phase III trial of "poor-risk" locally advanced NSCLC (RTOG 93-04) included just over 40% Karnofsky performance status 60-70 patients and showed median survival times of 9.5 and 10.3 months with 60 Gy of conventional radiation therapy alone or with recombinant β-interferon [18]. 1 year overall survival was just 44% in these patients.

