6.9.2 Esophagitis

Esophageal complaints are common with thoracic radiation therapy. Esophagitis does not constitute a reason to interrupt or delay radiotherapy provided oral intake is sufficient to maintain hydration. Patients should be advised to avoid alcoholic, acidic, or spicy foods or beverages. Viscous Xylocaine, Carafate, or other medications should be used for symptomatic relief. Occasionally, narcotics may be required.

It is not necessary to biopsy acute esophagitis in the first 2 weeks of therapy since it is rarely due to underlying viral or fungal disease. Acute esophagitis may persist for 4-6 weeks. If Grade 3 or 4 esophagitis occurs, and a treatment interruption is being considered, every effort should be made to limit it to 3 treatment days or less. Patients requiring hospitalization because of esophagitis may have their treatment interrupted. In this event, please notify [name].

Esophagitis should be graded according to the CTCAE v.4.0

Table 4. Esophagitis grading system

 	nagino grading oyotom
Grade	Clinical Scenario
1	Asymptomatic pathologic, radiographic, or endoscopic findings only
2	Symptomatic; altered eating/swallowing (e.g., altered dietary habits, oral
	supplements), IV fluids indicated <24 hrs
3	Symptomatic and severely altered eating/swallowing (e.g., inadequate oral
	caloric or fluid intake), IV fluids, tube feedings, or TPN indicated >24 hrs
4	Life-threatening consequences; urgent operative intervention indicated
5	Death

Treatment should be interrupted for grade 4 or greater dysphagia or odynophagia. Acute esophageal toxicity, which typically can occur within two weeks of the initiation of treatment and manifests as dysphagia, odynophagia, reflux symptoms, etc. should be pharmacologically managed with the following approach and should be initiated at the first signs or symptoms of esophageal toxicity. Recommended treatments are as follows:

- 1) Ketoconazole 200 mg PO q day OR Fluconazole 100 mg PO q day until the completion of radiation.
- 2) Mixture of: 2% viscous lidocaine: 60 cc, Mylanta: 30 cc, sucralfate (1 gm/cc): 10 cc; Take 15-30 cc PO q3-4 hrs prn. (Contraindications: pts on Dilantin, Cipro, Digoxin)
- 3) Ranitidine 150 mg PO BID (or other H2 blocker or a proton pump inhibitor such as omeprazole) until the completion of radiation
- 4) Grade 4 esophagitis: hold XRT until grade 2 or less. We expect a significant portion of patients will experience grade 3 esophagitis.

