9.9 Health-Related Quality of Life (HRQOL) Analysis

The study design is to prospectively analyze the QOL among patients with stage III NSCLC randomized between standard radiotherapy (60 Gy) versus hypofractionated IGRT radiation therapy. While hypofractionation is hypothesized to yield greater tumor cell kill, it may also increase the normal tissue toxicity, in which case there may be a decrease in HRQOL. The primary normal tissue toxicities in patients receiving radiation for lung cancer are esophagitis and pneumonitis. Prior studies have demonstrated that the most sensitive and clinically meaningful method for accurately capturing the normal tissue toxicities is via patients reported outcomes (PROs), such as HRQOL.

In this randomized trial, we plan to assess the FACT-TOI in all arms at 4 specific

time points to minimize patient burden: baseline (pretreatment), at the end of treatment (last day of treatment), and at the 6 and 12 month follow ups (See Appendix II). In order to analyze the difference in QOL between all arms, we plan to use a brief, validated instrument that is user friendly and has clinical relevance (the Lung Cancer Subscale of the FACT-TOI). FACT-TOI is a measure that sums the functional well being (FWB), physical well being (PWB), and the lung cancer subscale (LCS) of the Functional Assessment of Cancer Therapy - Lung (FACT-L) QOL instrument, which has been extensively used for measuring QOL in patients with lung cancer.[31] In a review of the literature reported that the FACT-L scale has been used in more than 5,000 patients and has been found to be sensitive to changes in performance status, treatment response.[32] FACT has been translated into 26 languages and is available free of charge to institutions with the completion of an agreement to share data, accessible at

http://www.facit.org/translation/licensure.aspx. The full FACT-L questionnaire can be completed in less than 10 minutes. This instrument has not only been shown to be prognostic for survival, but also sensitive to changes in QOL on serial evaluations throughout treatment. Importantly, the FACT-TOI has been associated with clinically meaningful changes in

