11.1.2.4 Toxicity: Grade 3-5 adverse events as graded by CTCAE v 4.0

11.2 Sample Size Determination

The sample size calculation is based on the primary endpoint, overall survival at 1 year, and the assumption that patients are randomized until the end of accrual. The sample size is calculated with the 2-sided significance level of 0.05 and 80% statistical power using a 2-sample log rank test. We assume that the overall survival function follows an exponential distribution for each arm. Accrual to the study is assumed to be uniformly distributed. The null hypothesis is that the there are no difference in 1-year survival rates between two arms. We assume that the patients will be accrued for 2 years with a 1-year follow-up. We hypothesize that the patients randomly assigned to the control arm and experimental arm have a 1-year survival rate of 45% (hazard rate [λc]) of 0.799) and 60% (hazard rate [λe]) of 0.511), respectively, which is translated to the hazard ratio of $\lambda e/\lambda c = 0.640$. One interim analysis and a final analysis are planned for early stopping for efficacy. The efficacy testing is based on the Lan-DeMets spending function, which resembles the O'Brien-Fleming boundary. The total sample size of 226 patients (113 in the control arm and 113 in the experimental arm) will be accrued to achieve the desired 80% statistical power and 2-sided significance level of 0.05. Guarding against ineligibility or lack-ofdata rate of up to 5%, the final targeted accrual for this study will be 238 patients (119 per arm). Sample size was estimated using the sample size software EaST version 5.

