11.5.7 Toxicity

Any subject who receives treatment on this protocol will be evaluable for toxicity. Each patient will be assessed for the development of toxicity according to the Time and Events table (Appendix II). Toxicity will be assessed according to the NCI Common Toxicity Criteria for Adverse Events (CTCAE), version 4.0. Dose adjustments should be made according to the system showing the greatest degree of toxicity.

Only adverse events assessed to be definitely, probably, or possibly related to protocol treatment will be considered. The rates of all Grade 3-5 adverse events, and death during or within 30 days of discontinuation of protocol treatment will be tested for equality using a two-sided chi-square test with a 0.05 significance level.

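### Severe toxicity and early death are formally compared only by a test of equality, with no between-arm estimate or confidence interval

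*Combined protocol and SAP*

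**What the plan says.** Comparing toxicity between the two regimens is a secondary objective (section 2.2.1). Section 11.1.2.4 makes it a secondary endpoint: "Toxicity: Grade 3-5 adverse events as graded by CTCAE v 4.0".

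Section 11.5.7 gives the analysis. The population is everyone treated: "Any subject who receives treatment on this protocol will be evaluable for toxicity". The events are restricted by attribution: "Only adverse events assessed to be definitely, probably, or possibly related to protocol treatment will be considered". Grade 3-5 events, and death during or within 30 days of stopping protocol treatment, "will be tested for equality using a two-sided chi-square test with a 0.05 significance level". That is the whole formal comparison. The section states no expected rate, power, effect measure or interval.

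Sections 11.5.1 and 11.5.6, by contrast, pair the log-rank test for overall survival, progression-free survival and time to local progression with Cox hazard ratios and 95% confidence intervals.

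The trial is sized on survival alone (section 11.2): "The total sample size of 226 patients (113 in the control arm and 113 in the experimental arm) will be accrued", raised to 238 (119 per arm) for ineligibility or missing data.

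**The concern.** Section 1.1 presents the newer techniques as a way "to allow a shorter overall treatment time without increasing toxicity". Section 9.9 concedes the opposite possibility: "While hypofractionation is hypothesized to yield greater tumor cell kill, it may also increase the normal tissue toxicity". If Arm A does better on survival, the next question is how much additional severe toxicity it may carry.

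A test of equality does not answer that. It gives a p-value, and p > 0.05 is compatible both with no increase and with a substantial one. Only an interval for the difference separates the two, and for toxicity the plan does not provide one. This gap exists whatever the true event rates are. The rates decide how often a real increase would go undetected.

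**Working it through.** **1. The number of patients behind the test.** Inputs from section 11.2: 1-year survival 45% vs 60%, two-sided 0.05, 80% power, 2 years of uniform accrual plus 1 year of follow-up, exponential survival.

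- HR = ln 0.60 / ln 0.45 = 0.511/0.799 = 0.640.
- Events (Schoenfeld) = 4(1.960 + 0.842)² / (ln 0.640)² = 157.3, so 158.
- Probability of death by the analysis = 1 − (e^(−λ) − e^(−3λ))/(2λ) = 0.775 (control) and 0.624 (experimental), mean 0.6997.
- N = 158/0.6997 = 226, and 226/0.95 = 238.

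The stated figures reproduce. No toxicity rate enters them, so the power of the toxicity test is whatever 113-119 per arm happens to give.

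**2. Which control rate?** None is stated for Arm B. The nearest figures are in section 1.2.

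- The preceding 15-fraction dose-escalation trial had 4 patients with grade 3 or higher treatment-related toxicity. The text says 52 patients, but the dose-level counts add to 18 + 23 + 21 = 62. Both are used: 4/52 = 7.7% and 4/62 = 6.5%.
- Another hypofractionated series reports 7% acute esophageal and 6% late pulmonary toxicity.
- A 30-patient trial reports at most 4/30 = 13.3%.

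All of these come from hypofractionated treatment, so using any of them for Arm B is an assumption. A range is shown.

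**3. How often the planned test misses an increase.** For each pair of true rates, binomial probabilities were summed over every possible pair of counts with n per arm. A table counts as significant if |p̂A − p̂B| / √[p̄(1 − p̄)(2/n)] > 1.96 (Pearson chi-square, no continuity correction). Miss rate = 1 − power.

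| Control vs experimental | Missed, 113 per arm | Missed, 119 per arm |
|---|---|---|
| *Doubling* | | |
| 6.5% vs 12.9% | 61.2% | 59.8% |
| 7.7% vs 15.4% | 54.6% | 53.5% |
| 10% vs 20% | 42.8% | 41.1% |
| 15% vs 30% | 22.1% | 19.8% |
| 20% vs 40% | 8.6% | 7.2% |
| *10-point rise* | | |
| 15% vs 25% | 53.0% | 50.6% |
| 20% vs 30% | 58.6% | 56.9% |
| 30% vs 40% | 65.2% | 63.2% |
| *Early death* | | |
| 3% vs 6% | 82.4% | 81.3% |
| 2% vs 5% | 79.3% | 78.2% |

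Power to detect a doubling passes 50% at a control rate of about 8.5% and 80% at about 15-16%. With a continuity correction, which section 11.5.7 neither specifies nor excludes, these become about 10% and 16-17%.

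**4. What an interval adds.** Suppose 17/113 (15.0%) in Arm A and 9/113 (8.0%) in Arm B.

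- Pearson chi-square = 2.78, p = 0.095: not significant.
- Difference = 7.1 points, Newcombe 95% interval −1.4 to +15.7 points.

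The planned output is the p-value. The interval shows that an excess of more than 15 points has not been excluded.

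**5. Precision available.** The half-width of a 95% interval with equal rates p is about 1.96√[2p(1 − p)/113]. At p = 8% this is 7.1 points, and at p = 20% it is 10.4 points.

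**The case against.** **The power figures depend on an assumed rate.** This stands. The cited low rates are not Arm B rates, and other parts of the protocol point higher. Section 6.9.2 says: "We expect a significant portion of patients will experience grade 3 esophagitis". The endpoint pools all related Grade 3-5 events, and section 7.0 allows concurrent chemotherapy in Arm B only. A reader might infer that a doubling would usually be missed. The documents do not support that without a condition: it holds only for control rates below about 8.5-9%. At 10% a doubling is found more often than not, and at 20% almost always. At those higher rates a doubling is a very large absolute increase, however, and a 10-point rise is the change more often missed.

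**Toxicity is not judged by this test alone.** This also stands. Yearly reports describe adverse event frequency and severity (11.5.8), the monitoring committee reviews adverse events quarterly (12.4), and patient-reported outcomes, which section 9.9 treats as the most sensitive measure of normal-tissue effects, have stated clinically relevant differences (9.9, 11.5.2). None of these supplies a between-arm estimate with an interval for Grade 3-5 events, so the point is confined to the formal comparison.

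**Nothing promises non-inferiority.** Correct. The phrase in section 1.1 about not increasing toxicity is background, the objective is only to compare, and the plan does not say how p > 0.05 will be read. A reader might infer that a binding margin is missing. The documents make no such claim, and give no control rate from which to set a margin. What remains is that a comparison is incomplete without an estimate and its uncertainty.

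**Conclusion.** The point holds for the formal comparison. As written, section 11.5.7 yields a p-value for severe related toxicity and for early death, and no statement of how large an increase the data can exclude. This does not depend on any assumed rate.

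The practical size does. With 113-119 per arm and an uncorrected chi-square, a doubling is missed about 54-61% of the time if the Arm B rate is 6.5-7.7%, and only 7-9% of the time if it is 20%. A 10-point rise from 15-30% is missed about 51-65% of the time. Early death is a rarer outcome, and on the illustrative rates a doubling from 3% is missed about four times in five. Every control rate here is an assumption.

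The documents do not show that the sponsor intends to read non-significance as similar toxicity. The risk is that the planned output leaves a reader little else to go on.

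**What to change.** In section 11.5.7, replace the sentence on testing for equality with wording such as:

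> For Grade 3-5 related adverse events, and separately for death during or within 30 days of discontinuing protocol treatment, the proportion of patients with the outcome will be reported by arm, with the risk difference (Arm A minus Arm B) and its two-sided 95% confidence interval (Newcombe or Miettinen-Nurminen). The two-sided chi-square p-value will be given as supporting information. A p-value above 0.05 will not be interpreted as showing similar toxicity.

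No margin is required, and neither the sample size nor data collection changes. The work is a wording amendment and one further calculation per outcome.

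The cost is in what can be claimed. With a half-width of about 7 points at 8% per arm and about 10 points at 20%, a statement of similar toxicity becomes harder to make. That reflects the information the trial will actually have.

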11.5.8 Interim Reports to Monitor the Study Progress

Interim reports with descriptive statistics will be prepared once a year until the initial paper reporting the treatment results has been accepted for publication. In general, the interim reports will contain information about the patient accrual rate with a projected completion date for the accrual phase; data quality; compliance rate of treatment delivery with the distributions of important prognostic baseline variables; and the frequencies and severity of adverse events. The interim reports will not contain results from the treatment comparisons with respect to the primary or secondary endpoints.

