6.1.5 Critical Structures and Constraints for Arm A

The following table lists maximum dose limits to a point or volume within several critical organs. Planning priorities are listed in Section 6.7.

Participating centers are encouraged to observe prudent treatment planning principles in avoiding unnecessary radiation exposure to critical normal structures irrespective of these limits.

In order to verify each of these limits, the organs must be contoured such that appropriate dose volume histograms can be generated. Instruction for the contouring of these organs will follow in section 6.5.

Dose constraints for the maximum dose allowed for several central chest structures are being modified because the tumor frequently abuts these structures, compliance testing in the initially treated patients showed that the original constraints could not be met, exceeding the constraints was not associated with toxicity in either the original phase I study patients or the patients initially treated on this protocol, and the proposed modified constraints still limit the dose to the prescription (i.e., avoids "hot spots"). The study committee agreed these changes are more reasonable and still maintain safety.

Dose volume limits for 15 fraction XRT:

Serial Tissue	Volume (cc)	Volume Max (Gy)	Max Point Dose (Gy)*	Endpoint (≥Grade 3)
Spinal cord	<5 cc	39 Gy	42.3 Gy	myelitis
Esophagus	<5 cc	51.3 Gy	55.3 Gy	stenosis/fistula
Brachial Plexus	<3 cc	44.5 Gy	50.6 Gy	neuropathy
Heart/Pericardium	<15cc	39.5 Gy	60 Gy	pericarditis
Great Vessels	<10 cc	48.9 Gy	60 Gy	aneurysm
Trachea and	<5 cc	39.5 Gy	60 Gy	stenosis/fistula
Large Bronchus		-		
Rib	<5 cc	48.9 Gy	60 Gy	pain or fracture
Skin	<10 cc	49 Gy	55.4 Gy	ulceration
Parallel Tissue	Critical	Critical	Other	Endpoint (≥Grade 3)
	Volume (cc)	Volume Dose	Constraints	
		Max (Gy)		
Lung (Right and	1500 cc	15.5 Gy	Mean dose	Basic Lung Function
Left minus GTV)	1000 cc	16.3 Gy	<18 Gy,	Pneumonitis
			V-18 <37%	

^{*} A maximum point dose is defined as the highest dose to 0.035 cc of tissue within the critical structure.

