11.5.9 Interim Analysis of Study Endpoints

There will be one interim analyses of the primary study endpoint (overall survival). The interim analysis will be conducted using Lan-DeMets alpha spending function when half of patients are followed-up for 1-year. The significance level will be calculated to ensure an overall significance level of 0.05 (type I error). In addition, a conditional power analysis will be performed at an interim efficacy analysis.[38] If the 95% confidence interval of the conditional power is less than 25%, then a recommendation for study discontinuation will be made to the Data and Safety Monitoring Committee (DSMC). The results of the interim analyses only will be reported, in a blinded fashion, to the DSMC. This analysis will also track the outcomes of the first 44 patients (enrolled when concurrent chemotherapy was not allowed) to subsequent patients performing sensitivity assessment regarding the need for a change in survival assumptions or a change in sample size.

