12.4 Data Management and Monitoring/Auditing

Trial monitoring will be conducted no less than annually and refers to a regular interval review of trial related activity and documentation performed by the DOT and/or the CRO Multi-Center IIT Monitor. This review includes but is not limited to accuracy of case report forms, protocol compliance, timeless and accuracy of Velos entries and AE/SAE management and reporting. Documentation of trial monitoring will be maintained along with other protocol related documents and will be reviewed during internal audit.

For further information, refer to the UTSW SCCC IIT Management Manual.

Toxicity and dose escalation reviews will be performed annually. These reviews will be documented by written reports that will be distributed to the distributed to the stud team.

The UTSW Simmons Comprehensive Cancer Center (SCCC) Data Safety Monitoring Committee (DSMC) is responsible for monitoring data quality and patient safety for all UTSW SCCC clinical trials. As part of that responsibility, the DSMC reviews all local serious adverse events and UPIRSOs in real time as they are reported and reviews adverse events on a quarterly basis. The quality assurance activity for the Clinical Research Office provides for periodic auditing of clinical research documents to ensure data integrity and regulatory compliance. A copy of the DSMC plan is available upon request.

The SCCC DSMC meets quarterly and conducts annual comprehensive reviews of ongoing clinical trials, for which it serves as the DSMC of record. The QAC works as part of the DSMC to conduct regular audits based on the level of risk. Audit findings are reviewed at the next available DSMC meeting. In this way, frequency of DSMC monitoring is dependent upon the level of risk. Risk level is determined by the DSMC Chairman and a number of factors such as the phase of the study; the type of investigational agent, device or intervention being studied; and monitoring required to ensure the safety of study subjects based on the associated risks of the study. Protocol-specific DSMC plans must be consistent with these principles.

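### No visible passage commits to giving the DSMC toxicity rates by arm before the final analysis, and 11.5.8 keeps the Grade 3-5 comparison out of the yearly reports

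*Combined protocol and SAP*

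**What the plan says.** Section 11.1.2.4 lists among the secondary endpoints "Toxicity: Grade 3-5 adverse events as graded by CTCAE v 4.0".

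Section 11.5.8 sets up the routine reports: "Interim reports with descriptive statistics will be prepared once a year". Their content includes accrual, data quality, treatment compliance "and the frequencies and severity of adverse events". The section ends with a restriction: "The interim reports will not contain results from the treatment comparisons with respect to the primary or secondary endpoints".

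Section 11.5.7 defines the between-arm toxicity analysis. Rates of treatment-related Grade 3-5 events, and of death on treatment or within 30 days of stopping it, "will be tested for equality using a two-sided chi-square test with a 0.05 significance level". It gives no interim timing.

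Section 11.5.9 says "There will be one interim analyses of the primary study endpoint (overall survival"), to be done when half the patients have one year of follow-up. It adds a conditional power assessment and a check of the survival assumptions. The interim results go to the DSMC in blinded form.

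Section 12.4 describes the other safety oversight. There is an annual toxicity review, of which it says: "These reviews will be documented by written reports that will be distributed to the distributed to the stud team". The DSMC sees serious adverse events as they are reported, reviews adverse events each quarter and holds a comprehensive review each year. A DSMC plan exists as a separate document, obtainable on request.

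**The concern.** A central safety question in this trial is comparative: does treatment in 15 larger fractions cause more severe toxicity than 30-33 standard fractions, or less? Section 9.9 itself raises the possibility of more normal-tissue toxicity with hypofractionation. Individual event reports and pooled frequencies cannot answer that question. It takes rates by arm, with the number at risk in each.

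A DSMC table with that content is not promised anywhere in the visible text, and the one explicit rule on the subject points the other way for the yearly reports. If the text is followed as written and nothing in the DSMC plan supplements it, the first planned comparison of Grade 3-5 rates is the final one.

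The point has some extra weight because section 6.1.5 records that several Arm A maximum-dose limits for central chest structures were changed during the trial. One of several reasons given is that "exceeding the constraints was not associated with toxicity in either the original phase I study patients or the patients initially treated on this protocol". A change that rests partly on early safety experience is a good reason to follow the later experience comparatively.

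**Working it through.** **1. Which documented routes could carry by-arm toxicity to the DSMC before the final analysis?**

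| Route | Section | Content | Recipient | By arm? |
|---|---|---|---|---|
| Yearly interim report | 11.5.8 | Adverse event frequencies and severity | Not stated | Comparisons of secondary endpoints barred; these include Grade 3-5 toxicity |
| Formal interim analysis | 11.5.9 | Overall survival, conditional power, survival assumptions | DSMC | No toxicity content specified |
| Annual toxicity review | 12.4 | Toxicity | Study team | Not stated |
| Quarterly adverse event review | 12.4 | Adverse events | DSMC | Not stated |
| Real-time event review | 12.4, 6.11 | Individual serious events | DSMC | Single reports, no denominators specified |
| Annual comprehensive review | 12.4 | Not stated | DSMC | Not stated |
| Toxicity test | 11.5.7 | Grade 3-5 rates, deaths to 30 days | Not stated | Yes, but no interim timing |

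One route is restricted, one is limited to survival, and the rest are silent. None commits to rates by arm with denominators.

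**2. When does the only formal interim look fall?**

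The planned size reproduces first. For 1-year survival of 45% and 60% the hazard ratio is 0.5108/0.7985 = 0.640. Schoenfeld's formula at two-sided 0.05 and 80% power gives 158 events. With exponential survival, 2 years of uniform accrual and 1 year of follow-up, the event probabilities are 0.775 and 0.624, mean 0.6997. So N = 158/0.6997 = 225.8, or 226, and 226/0.95 = 237.9, or 238. Both match section 11.2.

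At the 4 patients a month of section 11.3, half of the patients reach one year of follow-up at:
- N = 226: 113/4 + 12 = 40.25 months, with 4 × 40.25 = 161 enrolled (71%).
- N = 238: 119/4 + 12 = 41.75 months, with 4 × 41.75 = 167 enrolled (70%).

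That is about 80 per arm, and even then only survival is specified. Over the projected 60 months of accrual, 60/12 = 5 yearly reports would be issued under the 11.5.8 restriction.

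**3. What would a by-arm table add?**

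This is an illustration only. The documents give no toxicity rate by arm. I take 7.7% as an arbitrary reference rate for one arm, labelled neither A nor B. It is 4/52 from the dose-escalation trial in section 1.2, which used 15 fractions. The cohort sizes given there sum to 18 + 23 + 21 = 62, which would make it 4/62 = 6.5%. With 60 per arm (120/4 = month 30), I enumerated all binomial outcomes exactly and summed the probability that a two-sided Fisher test gives p < 0.05 with the second arm higher:

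| Rate in other arm | Pooled rate | Flagged, by-arm table |
|---|---|---|
| 12% | (7.7 + 12)/2 = 9.8% | about 6% |
| 15% | (7.7 + 15)/2 = 11.3% | about 16% |
| 20% | (7.7 + 20)/2 = 13.8% | about 40% |
| 25% | (7.7 + 25)/2 = 16.3% | about 66% |

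(Pooled rates use 4/52 unrounded.) With 6.5% as the reference, the last two rows become about 50% and 75%. With 80 per arm and 7.7%, they become about 55% and 81%. A pooled 13.8% looks the same whether the arms are at 7.7% and 20% or both at 13.8%, so the pooled column carries no information on the difference at any sample size.

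**The case against.** The strongest reply is that silence is not exclusion. Section 12.4 provides quarterly, annual and real-time DSMC review and describes none of it as pooled. Table content would normally sit in the DSMC plan, which is not reproduced here. A reader might infer that no planned report will show toxicity by arm. The documents do not support that: by-arm display is unspecified in 12.4, and 11.5.8 governs only the yearly reports.

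Second, 11.5.8 bars results of treatment comparisons, and 11.5.7 defines the toxicity comparison as a chi-square test. A descriptive table split by arm might therefore be allowed. That reading is possible. Pooling is the more natural reading of the bar, but it is not an explicit instruction, and the ambiguity is itself a reason to amend.

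Third, a reader might take the blinded reporting in 11.5.9 to mean that the DSMC is blinded to arm for safety. It applies to the interim analysis results, which are specified for survival. No passage masks treatment arm in the serious event reports, and the DSMC chair can act on them at once. This is real protection. It still does not supply a rate contrast.

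Fourth, a reader might infer from 6.1.5 that the Arm A limits were changed because no toxicity had been seen. The text says only that exceeding the limits was not associated with toxicity, and gives other reasons: tumours abut these structures, the earlier limits could not be met, and the new ones still cap dose at the prescription. It also shows that toxicity in patients on this protocol was being examined during the trial.

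**Conclusion.** The concern holds in a limited form. Section 11.5.8 read with 11.1.2.4 keeps the Grade 3-5 comparison out of the yearly reports, 11.5.9 looks at survival only, and nothing visible commits to giving the DSMC toxicity rates by arm with denominators before the final analysis. This rests on the text alone and is subject to the DSMC plan, which may already provide such a table. If it does, 11.5.8 needs to be reconciled with it.

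The size cannot be estimated from the documents. It would be tempting to put 7.7% in Arm B and 20% in Arm A and speak of 119 × (0.20 − 0.077), about 15, extra affected patients. That is not supported: the 7.7% comes from a 15-fraction trial, which is the Arm A approach, and the higher rate is invented. The direction is also open, because Arm B may receive concurrent chemotherapy, which section 1.1 associates with more toxicity, and section 6.9.2 expects a significant share of patients to have grade 3 esophagitis. The detection figures show that a by-arm table is informative for large differences and weak for small ones (about 6% at 12% against 7.7%). A pooled table is uninformative for all of them. This should be corrected, but given the real-time event review it does not show that patients are unprotected.

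**What to change.** 1. In 11.5.8, limit the bar to efficacy endpoints (overall survival, progression-free survival, time to local progression), quality of life and cost.
2. Add a closed, DSMC-only section to the yearly report and to the 11.5.9 package, giving by arm and with denominators: Grade 3-5 events, serious adverse events, and deaths within 30 days of treatment. State that the restriction to blinded reporting does not apply to this safety table.
3. In 12.4, name the DSMC as a recipient of the annual toxicity review, and say whether the quarterly adverse event review is by arm.
4. Check the DSMC plan and bring it and the protocol into agreement.
5. Keep tables for investigators and the study team pooled.

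The cost is a short amendment and one extra table from data already collected. The downside is small: someone must prepare the closed section and keep it confidential. No efficacy alpha is spent, because the table does not test overall survival.
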